SA 1 (primary): Eradication rate at one year will be compared between current recruits (i.e. study patients on adjuvant liquid alginate) and historical controls. Patients will be matched by type of therapy, and to the best of our ability, length of Barrett's.

SA2 (secondary): To compare the duration of treatment required to achieve complete endoscopic eradication of BE in patients treated with the combination of PPI and liquid alginate solution vs. those treated with PPI alone.

SA 3 (tertiary): To compare the number of treatment sessions required to achieve endoscopic eradication of BE in patients treated with the combination of PPI and liquid alginate solution vs. those treated with PPI alone.

Study Design

This is a pilot prospective cohort study at a single tertiary care center. Patients with BE and proven dysplasia (high or low grade) or risk of other abnormality presenting to our tertiary care center interested in endoscopic treatment will be asked to participate in the study. Participation will involve taking 10 mL of Gaviscon Advance four times daily along with twice daily PPI during the treatment duration. The control group will be a historical cohort of Barrett's esophagus patients treated in the last 5 years by the same endoscopists using similar approaches—these are patients who were prescribed twice daily PPI therapy alone during treatment.

Eligibility Criteria

Patients who are already scheduled for treatment of their dysplastic Barrett's esophagus or risk of other abnormality who are planning to undergo EMR, or ablation therapy with cryotherapy (spray or balloon) and/or RFA (with or without EMR) will be eligible for enrollment.

Inclusion criteria (all must be present):

- (1) Age ≥ 18
- (2) Patients already previously scheduled for treatment of complicated Barrett's esophagus
- (3) Long Segment Barrett's ($>3\text{cm}$)

Exclusion criteria:

- (1) Moderate to severe renal impairment, as defined by eGFR < 60 for 2 consecutive readings
- (2) Lack of capacity for decision-making
- (3) Allergy to hydroxybenzoates

- (4) Patients with uncontrolled hypertension or decompensated heart failure
- (5) Pregnancy- patients of child-bearing potential will be tested.
- (6) Patients with elevated calcium or potassium on screening laboratory testing (labs completed within the last month)

Enrollment

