We will compare the time to complete BE eradication/resolution (CRIM) between the prospective and historical cohorts using Kaplan-Meier time-to-event (time-to-CR) curves. The historical data maintained by the PI have n= 32 patients treated under similar conditions (e.g. facility, physicians) as the study patients who will be prospectively treated. As the purpose of this pilot study is to estimate the time to CRIM with the addition of liquid alginate for approximately 20 enrolled patients, no hypothesis testing will be performed to compare the distributions (hence, no power calculation). Comparisons will be descriptive only. Time-to-CR is assumed to be exponentially distributed and we will use the maximum likelihood estimate to estimate the rate parameter for each cohort. Patients who do not reach CR by the end of the study will be censored at that time. The difference in the rate parameter between cohorts will be calculated with a 95% confidence interval. Median time to CR will be estimated based on these parameters. Median time to CR under current treatments is about 22 months²⁷. If median time to CR with liquid alginate solution is sufficiently improved (e.g. to < 18 months), we will have high-quality pilot data with which to estimate a sample size for a more definitive randomized trial. Additionally, we will tabulate the number of treatments required to achieve CR and compare descriptively between cohorts as a secondary endpoint. Analyses above will also be stratified according to important covariates, such as disease grade and type of treatment (RFA or Cryotherapy).

Data Collection, Management, and Quality Control Procedures

Data entry will occur through RedCap, which will allow for study data to be directly entered into the database by the site via a secure internet connection. In addition to use of passwords and other security measures, all documents containing identifying information on individuals or physicians are considered confidential materials and will be safeguarded to the greatest possible extent. No information identifying a specific person, hospital, or physician will be released to or discussed with anyone other than study staff members. Appendix C shows the data points that will be collected from both the clinical and endoscopic visits.

Study Sites and Timeline

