A safety review committee will be assembled for this clinical study. This committee will be composed of 3 persons who are not study investigators. The overall goals of the committee will include the following: 1) identify unacceptably slow rates of accrual, 2) identify high rates of ineligibility, 3) identify protocol violations that suggest clarification of changes to protocol are needed, 4) identify unexpectedly high dropout rates that threaten the trial’s ability to produce credible results, 5) ensure the credibility of the study, 6) ensure the validity of study results, and most importantly, 7) protect the safety of trial participants. The safety review committee will meet quarterly. If irregularities are identified in any of the goal areas listed above, the committee will propose changes to the protocol or study infrastructure in order to remedy the problem. In the event of a severe problem, the committee may advise termination of the study.

Potential Problems and Pitfalls

There are several potential pitfalls that may affect this study. However, if these are anticipated and managed appropriately, we believe they will not significantly impact the validity of the findings.

We have been conservative with the estimate of the anticipated number of subjects during the funding period. There are typically only several patients at MUSC's GI clinic per month that present with dysplastic Barrett's (or Barrett's with IMC) who are naïve to treatment. Therefore, we are proposing a pilot study with a conservative initial enrollment goal of 20 patients. This number can be increased to compensate for subjects who are potentially withdrawn or LTFU. If this pilot study proves to be informative, a multicenter initiative would be the next step.

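### The plan does not require the 32 historical controls to be a complete, consecutive series listed and matched without knowledge of outcome

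*Combined protocol and SAP*

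**What the plan says.** The Study Design section defines the comparator: "The control group will be a historical cohort of Barrett's esophagus patients treated in the last 5 years by the same endoscopists using similar approaches". It adds that "these are patients who were prescribed twice daily PPI therapy alone during treatment". The Sample Size Calculation and Statistical Consideration section identifies the actual source: "The historical data maintained by the PI have n= 32 patients treated under similar conditions". The Endoscopic treatment section lists the PI among the endoscopists who treat study patients and decide on repeat procedures.

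Under Hypotheses & Specific Aims, all three aims are contrasts with patients on PPI alone. For the first aim, "Patients will be matched by type of therapy, and to the best of our ability, length of Barrett's". The statistical section does not mention matching again, so it is unclear whether 32 is the pool before or after matching.

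Potential Problems and Pitfalls describes patient flow: "There are typically only several patients at MUSC's GI clinic per month that present with dysplastic Barrett's". That count is limited to treatment-naïve patients and includes those with IMC. The enrolment goal is 20, and Study Sites and Timeline expects completion within two years.

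The documents do not give:
- calendar dates for the control window, or the dates that the 32 span;
- eligibility criteria for controls beyond the definition above;
- a statement that the 32 are consecutive;
- a count of patients left out, with reasons;
- any rule that controls be listed or matched without sight of outcome.

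**The concern.** A historical comparison depends on how patients entered the historical set. Here the set is kept by a clinician who also treats the prospective patients, its route of entry is not described, and the matching on segment length is discretionary. If patients with long or difficult courses are more likely to be in such a set, control eradication looks slow and alginate looks better than it is. If completed successes are over-represented, the error runs the other way.

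The planned analysis would not reveal either. The 95% confidence interval for the difference in rate parameters covers sampling error only. Stratifying by disease grade and type of treatment does not address who was recorded in the first place.

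The protocol's own numbers make completeness a fair question, because the controls accrued more slowly than the prospective patients are expected to, although the written control definition is the looser of the two.

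**Working it through.** The plan gives 32 as a bare count with no derivation, so there is no figure to reproduce. The check compares rates.

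**Inputs.** Controls: 32 (statistical section). Window: 5 years = 60 months (Study Design). Prospective goal: 20 (Potential Problems and Pitfalls). Study length: 2 years (Study Sites and Timeline). Clinic inflow: no number given, so 2 to 7 a month is assumed.

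**1. Control rate**, assuming the 32 span the whole window:
- 32/60 = 0.53 a month, or one every 60/32 = 1.9 months.

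**2. Planned prospective rate.**
- Enrolment over all 24 months: 20/24 = 0.83 a month; 0.83/0.53 = 1.6 times the control rate.
- Enrolment over 12 months, if every patient is to have the one-year primary outcome inside two years: 20/12 = 1.67 a month, or 3.1 times.
- At the control rate, 20 patients would take 20/0.533 = 37.5 months.

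**3. Criteria side by side.** Prospective patients must have "Long Segment Barrett's" (over 3 cm), pass the renal, cardiac, pregnancy, allergy and laboratory exclusions, and consent. The control definition states none of these. On paper the controls should be easier to accumulate, yet their rate is lower.

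**4. Against clinic inflow** (assumed values):

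| Inflow per month | Patients in 60 months | 32 as a share | 20 in 24 months as a share of inflow |
|---|---|---|---|
| 2 | 120 | 27% | 42% |
| 3 | 180 | 18% | 28% |
| 4 | 240 | 13% | 21% |
| 5 | 300 | 11% | 17% |
| 7 | 420 | 8% | 12% |

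The last column matters: the protocol's own target is also a minority of this inflow, so a low share does not by itself indicate selection.

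**5. Scale of the signal sought.** The statistical section cites a median of about 22 months under current treatment and gives under 18 months as an example of sufficient improvement. Under its exponential model, one-year eradication is 1 − 0.5^(12/22) = 31.5% against 1 − 0.5^(12/18) = 37.0% at the 18-month threshold, a gap of 5.5 points. In 32 controls that is 0.055 × 32 = 1.8 patients. This shows how few patients matter; it does not estimate any bias.

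**The case against.** The tempting stronger reading is that 32 controls against several new patients a month shows a hand-picked fraction. The documents do not support it. The inflow figure counts treatment-naïve patients who present to the clinic with dysplasia or IMC. The controls are patients actually treated, by the same endoscopists, with similar approaches, on PPI alone. The Enrollment section foresees patients on H2 blockers, and past patients on them could fall outside that definition. If the 3 cm limit was applied to controls as well, which is not stated, the pool shrinks again. A complete series of 32 is therefore possible. The inflow has no number, is worded to stress scarcity, and may not hold for the previous five years. Nor is it stated that the 32 span all 60 months. This objection stands, and it removes any claim that selection is demonstrated.

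A reader might also infer that the PI chose the controls knowing how they fared. The text says only that the PI maintains the data; knowledge of outcomes and outcome-based choice are not stated. Any figure for the resulting bias would need invented inputs, so none is offered here.

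Three further points limit the concern. Comparisons are declared descriptive and the study hypothesis-generating. The 22-month benchmark comes from a published source, not from the 32. Slow accrual is already among the safety review committee's goals. These lower the stakes but do not close the gap. The first aim is a direct comparison with the controls, a between-cohort difference with a confidence interval is planned, and the results are meant to inform a larger trial. The committee's remit on accrual does not touch control selection.

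**Conclusion.** The concern holds as a gap in design: the comparator for every aim is a PI-held set of 32, with no requirement that it be complete, consecutive, or listed and matched without knowledge of outcome. The protocol's figures make incomplete capture possible. The control rate is 0.53 a month, against at least 0.83 planned under stricter written criteria (1.6 times, or 3.1 times if enrolment must fit in 12 months). These ratios assume that the 32 span the full five years and that the two-year completion estimate is taken at face value. The 8% to 27% share of inflow rests on an assumed 2 to 7 patients a month and a different denominator, so it is background only.

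Selection is not shown, and the direction and size of any bias are unknown. The plan should be changed before the alginate data are analysed, because a better control cohort can be had at modest cost.

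**What to change.** Define the control cohort as every consecutive patient who:
- was first treated by the same endoscopists within a five-year window fixed by calendar dates;
- was on twice daily PPI alone during treatment;
- meets those prospective entry criteria that can be checked in the chart, including the segment length limit over 3 cm.

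Identify these patients from the existing endoscopy and pathology logs. Have an existing team member who has not seen outcomes fix the list, and any matching, before the alginate data are analysed. Report how many of the PI's 32 are on the list, and how many patients were excluded and why. Use the full consecutive set for the cohort comparison.

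The cost is extra chart abstraction by existing staff and a paragraph in the protocol. No new patients or procedures are needed. If the logs return the same 32, the check confirms the control group at little expense.

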Eligible patients who provide informed consent will be included in this prospective study and asked to take the alginate solution in addition to their twice daily PPI therapy. If patients are on concurrent H2 blocker therapy, this will be stopped after enrollment in the study. Subjects will be primarily recruited in the office setting, following decision to undergo ablation therapy. Upon the start of ablation therapy, patients will start taking 10ml of Gaviscon Advance 30 minutes after every meal and at bedtime (4 daily doses, after breakfast, lunch, dinner and before bed). This will begin on the day of the first endoscopy, after the ablation treatment. PPI therapy will continue as previously prescribed.

Endoscopic treatment

Standard guidelines will be followed for patients undergoing EMR, RFA or cryotherapy or RFA, up to 8-10 cm can be treated during one session and sessions are scheduled every 10-12 weeks. For cryotherapy, approximately the same area can be treated (8-10cm) during one session, and sessions are scheduled every 8-10 weeks. When initial EMR is performed, follow-up endoscopic ablative therapy will be scheduled approximately 8 weeks later. The decision of which therapy to implement depends largely on anatomy and patient preference and will be determined by the endoscopists involved in the study—[name] (PI), [name], or [name]. Furthermore, all decisions pertaining to the need for repeat procedures to address inadequate treatment or incomplete tissue sampling, or the decision to refer for the alternate procedure, will be dictated by the above endoscopists. As mentioned previously, number of sessions to achieve complete eradication of Barrett's varies by length, but on average can take anywhere from 3-5 sessions, depending on initial length of BE as well as existence and size of hiatal hernia³¹.

Follow-up Assessments

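### Time to CRIM is summarised by an unchecked constant-hazard model that the treatment schedule contradicts, so the fitted rate and median depend on follow-up length, with bias in either direction

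*Combined protocol and SAP*

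**What the plan says.** Under Sample Size Calculation and Statistical Consideration, the combined protocol and SAP plans Kaplan-Meier curves for both cohorts but takes its numerical summaries from a parametric model: "Time-to-CR is assumed to be exponentially distributed and we will use the maximum likelihood estimate to estimate the rate parameter". From that fit, "The difference in the rate parameter between cohorts will be calculated with a 95% confidence interval" and "Median time to CR will be estimated based on these parameters". On censoring: "Patients who do not reach CR by the end of the study will be censored at that time". No fit check, alternative model or fallback is given, and the Kaplan-Meier curves are not named as a check or as the source of the median.

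The same section says that "the purpose of this pilot study is to estimate the time to CRIM with the addition of liquid alginate". It cites a median of about 22 months under current treatment and looks ahead to a randomized trial: "If median time to CR with liquid alginate solution is sufficiently improved", with under 18 months as the example.

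Under Endoscopic treatment, cryotherapy sessions are 8-10 weeks apart and RFA sessions 10-12 weeks apart. After initial EMR, "follow-up endoscopic ablative therapy will be scheduled approximately 8 weeks later". Eradication "on average can take anywhere from 3-5 sessions, depending on initial length of BE". Follow-up Assessments and Outcomes require both endoscopic appearance and biopsy before CRIM is declared.

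**The concern.** An exponential model gives a patient the same chance of CRIM on every day from time zero. Here the event can be recorded only at an endoscopy, the first scheduled return is about 8 weeks out, and several sessions are usually needed. Time zero is not defined. If it is first treatment, the hazard is zero at first and probably low for some time after. If some patients never respond, it also falls later on.

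When the hazard is not constant, the fitted rate is an average over whatever follow-up was observed, so two cohorts with the same true distribution but different follow-up get different fitted rates. Different follow-up is plausible here. Enrolled patients enter over time in a study expected to finish within 2 years (Study Sites and Timeline), while controls were treated over the last 5 years (Study Design).

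Time to CRIM is a secondary outcome, but H1 is about speed, and the fitted median is offered as input for sizing the next trial. With no hypothesis test planned, the estimates are the product of this analysis.

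**Working it through.** **Formulas.** Rate r = events / total follow-up time. Median = ln 2 / r. P(CRIM by t) = 1 − 2^(−t/median). Standard error of the rate difference = √(r₁²/d₁ + r₂²/d₂), where d is the number of events.

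**The plan's own figure.** No power or event calculation exists to reproduce, and the 22-month median is a cited value. Under the model it means r = 0.693/22 = 0.0315 per month.

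**Step 1: the first 8 weeks.** 8 weeks = 1.84 months. At a 22-month median the model puts 1 − 2^(−1.84/22) = 5.6% of patients with CRIM in a period when none can be recorded.

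**Step 2: fit against truth, 24-month follow-up for all.** Assumed: 3, 4 or 5 intervals equally likely, each drawn afresh from 8-12 weeks. Mean time is 4 × 10 = 40 weeks = 9.2 months. With a proportion p never responding, follow-up time per event is 9.2 + 24p/(1 − p) months. For p = 0 the fitted median is 0.693 × 9.2 = 6.4. For p = 0.2 it is 0.693 × (9.2 + 6.0) = 10.5. Simulation agrees and supplies the true values:

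| Non-response | Fitted / true median (months) | Fitted / true 12-month CRIM (%) |
|---|---|---|
| 0% | 6.4 / 9.2 | 73 / 93 |
| 10% | 8.2 / 9.4 | 64 / 84 |
| 20% | 10.5 / 9.8 | 55 / 75 |
| 30% | 13.5 / 10.8 | 46 / 65 |

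The 93% depends on the fresh spacing draw at each session. With one spacing per patient it is 87%, and the gap falls from 20 to 14 points. With 1-7 intervals equally likely, the fitted 12-month figure runs from 2 points low to 4 points high.

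**Step 3: unequal follow-up.** Both cohorts have the same true distribution. Controls are followed for 0-60 months. The study lasts 24 months, with entry over 12 months (follow-up 12-24) or over 24 months (follow-up 0-24). Fitted medians in months:

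| Scenario | Enrolled, 12-month entry | Enrolled, 24-month entry | Controls |
|---|---|---|---|
| True median 22, 8-week delay, no non-responders | 23.1 | 24.6 | 22-23 |
| True median 22, 22-week delay, no non-responders | 25.6 | 29.9 | 22-23 |
| 3-5 intervals, 10% non-response | 7.8 | 9.8 | 9.7 |
| 3-5 intervals, 20% non-response | 9.5 | 11.7 | 13.1 |
| 3-5 intervals, 30% non-response | 11.8 | 14.1 | 17.5 |

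The sign changes because two effects compete. The initial delay is a larger share of a short follow-up, which slows the fitted rate. Each non-responder adds event-free time for as long as follow-up lasts: on average 18 months (12-month entry), 12 months (24-month entry) or 30 months (controls). Hand check at 20% with 12-month entry, taking every responder as reaching CRIM before censoring: 0.693 × (9.2 + 18 × 0.2/0.8) = 0.693 × 13.7 = 9.5.

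**Step 4: intervals and the benign case.** In the delay scenarios with 20 against 32 patients, the 95% interval for the rate difference covers the true value in 95.6% (12-month entry) and 93.7% (24-month entry) of trials with the 8-week delay, and in 95.6% and 90.0% with the 22-week delay. With a fixed 24 months in both cohorts, the fitted medians are 22.6 and 23.5 for a true 22, and coverage is 96.2% and 97.5%.

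**The case against.** The case for leaving the plan alone has substance. This is a descriptive pilot without testing. The primary outcome, CRIM at one year, does not use the model. Kaplan-Meier curves will be drawn, so a gross misfit would be visible. The 18-month figure is an example and not a decision rule. With about 20 patients, a one-parameter model is a defensible choice. Sampling noise is also large: with a truly exponential 22-month median, 95% of fitted medians from 20 patients fall between about 12 and 52 months (12-month entry) or 11 and 66 (24-month entry). A bias of 1-3 months, as with the 8-week delay, is small against that. If every enrolled patient is followed to resolution, as Follow-up Assessments says, the censoring part of the error shrinks.

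All of that stands, and it limits the size of the point. It does not answer it: the median and the rate difference still come from the fit, and the planned curves have no stated role in checking it.

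A reader might go further and infer that shorter follow-up of enrolled patients must make alginate look slower. The documents do not support that. It follows only if there is a delay and no, or very few, non-responders; with 20-30% non-response the enrolled cohort looks faster. Nor are 3-5 sessions a minimum and maximum. They are a range of averages, so CRIM before the third session cannot be ruled out.

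**Conclusion.** The point holds, at moderate weight. A constant hazard from first treatment conflicts with the protocol's own schedule, and nothing in the plan would detect or handle the misfit.

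Its size and direction rest on assumptions that the documents do not settle: time zero, spread of session counts, non-response, entry pattern and length of historical follow-up. Across the cases examined, two identical cohorts can show fitted medians several months apart in either direction. The 12-month CRIM implied by the fit can miss the directly counted primary outcome by up to about 20 points, or by almost nothing. The session-based cases have true medians of about 9-13 months, well below the cited 22. At 22 months the bias is about 1 month with a common 24-month follow-up and about 1-3 months with staggered entry and an 8-week delay.

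The consequence falls on the median and rate difference intended for planning the next trial.

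**What to change.** Revise the statistical section as follows.

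1. Take the main time-to-CRIM estimates from the planned Kaplan-Meier curves: cumulative CRIM at 12 months and restricted mean time to CRIM up to 12 months, per cohort and as a difference with a 95% interval, with the same horizon in both cohorts. For cumulative CRIM, use log-log limits per cohort and combine them for the difference.
2. Report the Kaplan-Meier median if reached, otherwise state 'not reached'.
3. Keep the exponential rate and median as a sensitivity analysis drawn over the Kaplan-Meier curve. State that they will not be used for planning if the fit is visibly poor, for example if the fitted curve leaves the Kaplan-Meier confidence band.
4. Define time zero and report follow-up length for each cohort.

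This changes wording only; data and curves are the same. In the 22-month delay simulations the Kaplan-Meier 12-month estimate was within 0.002 of the truth. The combined log-log interval for the difference covered in 95.8-97.4% of trials and was undefined in 0-3%, mainly where one cohort had no CRIM by 12 months.

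There are costs. At a 22-month median with staggered entry, the Kaplan-Meier median is reached in only 46-51% of enrolled cohorts, and is then typically 16-18 months because only fast cohorts reach it. It should not be used alone to judge improvement. Plain restricted-mean intervals run slightly narrow (91-94% coverage). The change removes bias but adds little ability to separate the cohorts.
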